10.2.4. Reporting Requirements for Serious Adverse Events (SAEs)

All SAEs regardless of causality will be reported by the investigator to the Sponsor through the 30-day period after the last dose of study treatment. Deaths and SAEs occurring after the 30-day safety follow-up period AND considered related to study treatment or study procedures must also be reported until the end of the study or subject death.

Report all SAEs (initial and follow-up information) on the SAE Report form and email it to the Sponsor's Pharmacovigilance group or designee, within 24 hours of learning of the event or information (see below). The Sponsor may request follow-up and other additional information from the investigator (eg, hospital admission or discharge notes, laboratory results).

Sponsor's Pharmacovigilance Group Contact Information					
PRIMARY CONTACT: email	[contact]				

Report all deaths with the primary cause of death as the SAE term, as death is the outcome of the event, not the event itself. If an autopsy was performed, report the primary cause of death on the autopsy report as the SAE term. Forward autopsy and postmortem reports to the Sponsor's Pharmacovigilance group or designee, as outlined above.

If study treatment is discontinued, temporarily suspended, or dose reduced because of an SAE, include this information in the SAE Report form.

Suspected Unexpected Serious Adverse Reactions (SUSARs) are SAEs that qualify for mandatory expedited safety reporting to regulatory authorities where the SAE is suspected to be caused by the study treatment and is considered unexpected (ie, not listed as expected in the Reference Safety Information section of the current IB, clinical study protocol, or approved

labeling for marketed drugs). In this case, the Sponsor's Pharmacovigilance group or designee will report to the relevant regulatory authorities and forward a formal notification describing the SUSAR to investigators, according to regulatory requirements. Each investigator must then notify his or her IRB/IEC of the SUSAR as required by local regulatory authorities and in accordance with IRB/IEC policy.

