10. EVALUATION, RECORDING, AND REPORTING OF ADVERSE EVENTS

10.1. Definitions

10.1.1. Adverse Event (AE)

An AE is any untoward medical occurrence associated with the use of a drug in humans, whether or not considered drug related. An AE can therefore be any unfavorable and unintended sign (including a clinically significant abnormal finding in laboratory tests or other diagnostic procedures), symptom, or disease temporally associated with the use of a drug, without any judgment about causality. An AE can arise from any use of the drug and from any route of administration, formulation, or dose, including an overdose.

Disease progression is not considered to be an AE or SAE. If there are specific AEs that are always part of disease progression, these do not need to be reported as AEs or SAEs. Pre-existing medical conditions (other than natural progression of the disease being studied) judged by the investigator or subject to have worsened in severity or frequency or changed in character during the protocol-specified AE reporting period will be reported as AEs or SAEs as appropriate.

An AE or SAE can also be a complication that occurs as a result of protocol mandated procedures (eg, invasive procedures such as biopsies).

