10.1.2. Serious Adverse Events (SAEs)

An AE is considered serious, if in the view of either the investigator or sponsor, it results in any of the following outcomes:

- Death.
- A life-threatening AE.

An AE is considered "life-threatening" if in the view of either the investigator, or sponsor, its occurrence places the subject at immediate risk of death. It does not include an AE that, had it occurred in a more severe form, might have caused death.

- Inpatient hospitalization or prolongation of an existing hospitalization.
- A persistent or significant incapacity or substantial disruption of the ability to conduct normal life functions.
- A congenital anomaly or birth defect.

Important medical events that may not result in death, be life-threatening or require hospitalization may be considered serious when, based on the appropriate medical judgment, they may jeopardize the subject and may require medical or surgical intervention to prevent one of the outcomes listed in the definition of SAE. Examples of such medical events are intensive treatment in an emergency room or at home; blood dyscrasias or convulsions that do not result in inpatient hospitalization; or development of drug dependency or drug abuse.

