10.2. Adverse Event Reporting and Descriptions

Record new AEs from the start of study treatment until 30 days after the last dose of study treatment or until the subject starts new anticancer treatment, including new investigational treatment, whichever occurs first. Also record screening procedure-related AEs that occur before the start of study treatment. Collection of AEs may also continue until the decision is made to permanently discontinue study treatment.

Record all AEs either observed by the investigator or one of the medical collaborators, or reported by the subject spontaneously, or in response to the direct question below, in the AEs section of the subject's eCRF, in the source document, and if applicable, record on the SAE Report form. Whenever possible, the investigator should group signs and symptoms (including laboratory tests or other results of diagnostic procedures) into a single diagnosis under a single term. For example, cough, rhinitis, and sneezing might be reported as "upper respiratory infection" or a pulmonary infiltrate, positive sputum culture and fever might be reported as "pneumonia."

To optimize consistency of AE reporting across centers, ask the subject a standard, general, non-leading question to elicit any AEs (such as "Have you had any new symptoms, injuries, illnesses since your last visit?").

Death is an outcome of an SAE and usually not itself an SAE, unless it is death with no identifiable cause or event. In all other cases, record the cause of death as the SAE. Investigators will assess the status of previously reported, and occurrence of new AEs and SAEs at all subject evaluation time points during the study.

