#### 7.6.2 Adverse Events

Adverse events reported by study subjects or observed by investigators will be mapped to the appropriate System Organ Class (SOC) and Preferred Term (PT) according to the Medical Dictionary for Regulatory Activities (MedDRA). Severity of AEs will be graded using Common Terminology Criteria for Adverse Events (CTCAE) version 4.03 (protocol Appendix 2).

TEAEs are defined as events that first occurred or worsened on or after the date of the first dose of study treatment until 30 days after the last dose of study treatment or until the start of a post-treatment alternative anti-cancer treatment, whichever occurs first, with the following exceptions: events that occurred after 30 days beyond the last dose of study treatment or the start of a post-treatment alternative anti-cancer treatment will also be considered treatment-emergent if the events are both serious and related to the study treatment. For the purpose of determining whether an AE is a TEAE, incomplete AE start and stop dates will be imputed conservatively following the data programming conventions as detailed in the Taiho Data Programming Standards.

All AE data collected in the study database with an AE start date on or before the data cutoff date will be included in the data listings, including those that are not treatment emergent. Only TEAEs will be included in the AE summary tables.

An overall safety summary table containing counts and percentages of subjects with any AE, any AE Grade ≥3, AE leading to treatment discontinuation, any SAE, and subcategories of SAEs (fatal SAEs) will be produced.

Related events are those that the Investigator considered to be related to study treatment as described in the study protocol. All summaries of AEs will be summarized by cohorts and all cohorts combined within regimen within parts (A&B), and within Phase (I&II). Tables may be combined when space allows.

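### Protocol 10.1.1 conflicts with 10.2 and 10.2.4 on whether death from progression is an SAE, so some all-causality SAE and AE counts can depend on which section a site followed

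*Protocol*

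**What the plan says.** Four protocol passages and one SAP section bear on this.

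- Protocol 10.1.1: "Disease progression is not considered to be an AE or SAE". It adds: "If there are specific AEs that are always part of disease progression, these do not need to be reported as AEs or SAEs". It makes no exception for progression that is fatal.
- Protocol 10.1.2 builds seriousness on an AE: "An AE is considered serious, if in the view of either the investigator or sponsor, it results in any of the following outcomes". Death is the first outcome listed.
- Protocol 10.2 sets aside death with no identifiable cause and then says: "In all other cases, record the cause of death as the SAE".
- Protocol 10.2.4: "Report all deaths with the primary cause of death as the SAE term". Where there was an autopsy, its primary cause becomes the SAE term. The same section sets the any-cause reporting window, which closes 30 days after the last dose. Beyond that, only deaths and SAEs related to treatment or study procedures are reportable.
- SAP 7.6.2 plans an overall safety table that includes any AE of Grade 3 or higher and "any SAE, and subcategories of SAEs (fatal SAEs) will be produced". It also plans a summary of AEs with fatal outcome. It gives no rule to keep, remove or separate progression terms.

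**The concern.** Inclusion criterion 3 admits subjects whose disease is refractory or relapsed, or who have no available therapy. Protocol 5.4.1 says subjects who progress should not stay on treatment. For them, the 30-day any-cause SAE window opens when death from the cancer is most plausible, so this is a foreseeable case rather than an odd one.

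If two sites handle it differently, one enters no SAE and the other enters a fatal, Grade 5 event. The pooled count then depends partly on reporting practice. There is no control arm in which the same inconsistency would also appear, and AE incidence is part of the Phase 1 primary endpoint (Protocol 4.3.1).

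**Working it through.** The documents state no fatal-SAE rate, so there is no figure to reproduce. The check is a comparison of texts, followed by an illustration of scale.

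**1. One subject, each section read literally.** The subject dies of the cancer under study 20 days after the last dose.

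| Section | Result |
|---|---|
| Protocol 10.1.1 | Progression is not an AE, so no SAE |
| Protocol 10.1.2 | An SAE must be an AE, so no SAE if 10.1.1 governs |
| Protocol 10.2 | The cause of death is identifiable, so it is recorded as the SAE |
| Protocol 10.2.4 | A death within the window, so it is reported with its cause as the SAE term |

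The rules give opposite answers, and no sentence says which prevails. The protocol does write such an exception elsewhere: Protocol 7.4 takes events with a clear alternative cause, such as progression, out of the DLT definition.

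**2. Which deaths are in play.** Only deaths on treatment or within 30 days of the last dose. Later progression deaths are not reportable under either reading. The SAP tables count only treatment-emergent events, so events that begin after a new anticancer therapy has started also drop out unless they are serious and related.

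**3. Which outputs move.**
- Exposed: any SAE, fatal SAE, AE with fatal outcome, and AE of Grade 3 or higher, all regardless of causality. The any-SAE and Grade 3 or higher counts change only for subjects with no other qualifying event.
- Not exposed: related AEs and SAEs (SAP 7.6.2), deaths and causes of death (SAP 7.6), the death listing with primary cause (SAP 7.0), 30- and 60-day all-cause mortality from death dates (SAP 7.6.4), DLTs, ORR, PFS and OS.

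**4. Scale, by assumption.** Let d be the proportion dying in the window, s the share of those deaths due to progression, and q the share of progression deaths that sites report as SAEs. Assume every other death in the window is a fatal SAE. Then

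fatal-SAE rate = d × [(1 − s) + q × s].

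The values of d and s below are assumptions; the documents give neither. The total of 300 is the planned maximum in Protocol 4.1.

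- d = 10%, s = 80%: q = 0 gives 10% × 0.20 = 2% (6 of 300); q = 1 gives 10% (30 of 300); q = 0.5 gives 2% + 0.5 × 8% = 6% (18 of 300).
- d = 5%, s = 60%: 5% × 0.40 = 2% against 5%.
- d = 15%, s = 90%: 15% × 0.10 = 1.5% against 15%.

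A second set of assumptions puts deaths from other causes at about 2% and progression deaths in the window at 5%, 10% or 20%. For the 180 planned Phase 2 subjects, the rate is 4/180 = 2.2% if none of the progression deaths is reported. It is 13/180 = 7.2%, 22/180 = 12.2% or 40/180 = 22.2% if all are, and 4.7%, 7.2% or 12.2% if half are. For one cohort of 29, it is 1/29 = 3.4% against 2/29 = 6.9%, 4/29 = 13.8% or 7/29 = 24.1%.

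Reporting progression deaths can only raise the count. How far it raises it rests entirely on the assumed inputs.

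**The case against.** The strongest reply is that the sections can be read together. An SAE must first be an AE (10.1.2), and progression is not one (10.1.1). Protocol 9.3.1 also leaves the primary disease out of the worsening conditions to be recorded. On that view 10.2 and 10.2.4 are naming rules: they tell sites to enter the cause rather than the word death for events that are already SAEs. Even in 10.2.4 the reference to all deaths is not fully literal, because unrelated deaths after 30 days are not reportable. SAEs also go to a central pharmacovigilance group, which can ask for more information.

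This is a sensible reading and may be the intended one. But the protocol does not state it, and the words of 10.2 and 10.2.4 point the other way. Section 10.2.4 also names deaths beside SAEs when it describes reporting after 30 days. A careful site could follow either reading.

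A reader might infer more: that the SAE rates cannot be read as a safety result at all, or that sites did in fact differ. The documents support neither. The unaffected outputs listed above still separate toxicity from disease, and nothing shows how sites actually reported. The two ends of each range contrast every site following one reading with every site following the other; mixed practice falls between them.

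**Conclusion.** The conflict is real but limited. For progression deaths on treatment or within 30 days of the last dose, the protocol gives two answers and leaves the reconciliation unstated. The SAP carries the ambiguity into four all-causality counts, which should not be read on their own. Efficacy results, dose decisions based on DLTs, related-event tables and mortality do not depend on it.

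The size is unknown. The 2% to 10% range for the fatal-SAE rate gives outer bounds under assumed values (10% dying in the window, 80% of them from progression). It is not an estimate for this trial. The point is worth correcting because it can change reported safety counts and is cheap to settle.

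**What to change.** **Protocol.** State one recording rule for death due to progression of the cancer under study, and use it in 10.1.1, 10.2 and 10.2.4. Either rule works for the analysis if applied uniformly. Protocol 14.4 lets administrative letters correct inconsistencies, so a letter may suffice.

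**SAP 7.6.2.** Show the any-SAE, fatal-SAE and fatal-AE counts with and without progression-term events, with those events on their own line, and apply the same split to AEs of Grade 3 or higher. Define the progression terms in advance. Check each fatal event against the planned listing of primary cause of death. The count without progression terms is then comparable across sites. The count with them becomes comparable only if progression deaths in the window that were never entered as SAEs are added from that listing.

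The SAP change does most of the work. The study began in Q2 2018 (SAP 6.0), and adding the planned 61 months gives about mid-2023, before the SAP's approval date of 2 April 2024. If those durations held, most reporting predates any new protocol wording.

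**Cost.** Two protocol clauses or one letter, one or two SAP sentences with a term list, and a query on deaths already reported in the window. No new data collection is needed, since the cause of death is already to be listed.

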10.3. Follow-up for Adverse Events

Follow all AEs and SAEs that are encountered during the protocol-specified AE reporting period (1) to resolution, (2) until the investigator assesses the subject as stable and the event is following a clinically expected outcome, or (3) until the subject is lost to follow-up or withdraws consent.

11. STATISTICS

Statistical analyses will be performed by the Sponsor or its designee.

Data summaries and listings will be generated using SAS version 9.4 or a more recent version (SAS Institute Inc., Cary, NC, USA).

The statistical analysis plan and/or the clinical study report will provide additional details of the analysis, which may include details of missing and, if applicable, unused data, as well as additional sensitivity analyses of the primary and secondary variables. The clinical study report will describe deviations from the statistical analysis plan, if any.

11.1. Sample Size

The dose-escalation part of the study (Phase 1 Part A) follows a standard 3+3 study design, with a cohort size of 3 or 6 evaluable subjects. Dose escalation will continue until the MTD for each regimen evaluated is determined. Evaluable subjects for dose-escalation decisions in Part A are those who have completed the first cycle and have received at least 85% of planned doses in the first cycle of treatment (or were not able to receive at least 85% of planned doses due to safety concerns).

For Part B (of Phase 1), a sample size of 14 evaluable subjects will ensure a 90% probability of observing at least 1 adverse reaction to treatment for any adverse reaction with a $\geq 15\%$ incidence. Evaluable subjects for Part B are all subjects who receive any amount of study drug.

For Phase 2, the sample size is based on a Simon's Optimal 2-stage design (Simon 1989). Each cohort will enroll 10 subjects into the first stage. Should ≥ 2 first-stage subjects respond, an additional 19 subjects will be enrolled into the second stage. Therefore, up to 29 subjects will be used for each treatment cohort. The sample size, (10+19) 29, under this Simon's Optimal 2-stage design, will achieve a power of 80% to test the null hypothesis of ORR $p_0 \leq 0.1$ at a 1-sided alpha of 0.05 assuming the response rate p_1 is 0.3. For Stage 2, the null hypothesis will be rejected if ≥ 6 responses are observed in a cohort of 29 subjects. For Cohort F (which will enroll patients with various tumor types and gene aberrations [Table 2]), the sponsor, with approval of the DSRC, may expand enrollment for a particular molecularly defined subpopulation in which the most number of responses are observed to 10 or 29 subjects under the same Simon's Optimal 2-stage design as for the other cohorts for better assessment of activity in that disease subpopulation (Optional Cohort F expansion). It is expected that no more than 2 subpopulations will be expanded in this manner.

11.2. Analysis Sets to Be Analyzed

11.2.1. All Subject Analysis Set

The All Subject Analysis Set will include information from all screened subjects, including those who did not meet the study entry criteria or did not receive a study treatment. This data set will only be used for disposition in which all screened subjects are accounted for.

11.2.2. Efficacy Analysis Set

The Efficacy Analysis Set will include all subjects who receive any amount of study treatment for efficacy analyses. Efficacy analyses will be based on the actual treatment received. The ORR and DCR analysis will be based on subjects who are in the Efficacy Analysis Set and who had disease assessment at baseline and at least 1 follow up disease assessment or subjects who died or stopped treatment before the first scheduled disease assessment due to clinical progression or toxicity.

11.2.3. Safety Analysis Set

The Safety Analysis Set will include data from all subjects who receive any amount of study drug. Safety analysis will be based on the actual treatment received. All data will be included, and no subjects excluded because of protocol violations.

11.2.4. PK Analysis Set

The PK Analysis Set will consist of all available plasma concentrations and PK parameters for ASTX029 from subjects who have received study drug and for whom PK samples were collected and successfully analyzed.

11.2.5. Pharmacodynamic and Biomarker Analysis Set

Subjects will be included in the pharmacodynamic and biomarker analyses if they have received study drug and their samples were successfully collected and analyzed.

11.3. Schedule of Analyses

This is an open-label study. Ongoing analyses to help manage the study and support the DSRC reviews for safety and antitumor activity will be undertaken. A final analysis will be conducted after all subjects have completed the study.

11.4. Disposition

The number and percentage (n, %) of subjects enrolled, treated, lost to follow-up, and withdrawn from treatment or discontinued from the study (with reason) will be summarized. The sample sizes for the Efficacy Analysis Set, Safety Analysis Set, PK Analysis Set, and Pharmacodynamic and Biomarker Analysis Set will be clearly identified. All subjects in the All Subject Analysis Set will be included in the disposition analysis.

Summaries will be provided separately for each regimen in Phase 1 Part A, for the RDE cohort(s) in Phase 1 Part B, and for the RP2D in Phase 2.

11.5. Analysis of Demographic and Baseline Data

Subject demographic and baseline characteristics will be summarized by mean, standard deviation, median, minimum, and maximum for continuous variables; and by counts and percentages for categorical variables. All subjects who received any amount of study drug (ie, the Safety Analysis Set) will be included in the analysis of demographic and baseline characteristics.

Summaries will be provided separately for each regimen in Phase 1 Part A, for the RDE cohort(s) in Phase 1 Part B, and for each cohort in Phase 2.

11.6. Efficacy Analyses

Analyses for all efficacy endpoints will be provided separately for each treatment regimen in Phase 1 Part A and for the RDE cohort(s) in Phase 1 Part B, and for each cohort in Phase 2.

11.6.1. Objective Response and Disease Control Rate

The ORR will be calculated as the number of evaluable subjects whose best response is CR or PR, divided by the total number of subjects evaluable for ORR analysis (Section 11.2.2). The DCR will be calculated as the number of subjects whose best response is CR, PR, or stable disease (SD), divided by the total number of subjects evaluable for DCR analysis (Section 11.2.2). The 90% Clopper-Pearson confidence intervals (Cis) for the ORR and DCR will be provided.

11.6.2. Progression-free Survival

The PFS is defined as the number of days from the start of the study treatment to disease progression or death, whichever occurs first. The PFS will be analyzed using a Kaplan-Meier method, with PFS time being censored on the date of the last disease assessment. The 90% CI for median PFS will be provided using the Kaplan-Meier procedure. All subjects in the Efficacy Analysis Set will be included in the PFS analysis.

11.6.3. Overall Survival

The OS is defined as the number of days from the day the subject was randomized to the date of death (regardless of cause). Subjects without a documented death date will be censored on the last date they were known to be alive. The OS will be presented using a Kaplan-Meier estimate. The 90% CI for median OS will be provided using the Kaplan-Meier procedure. All subjects in the Efficacy Analysis Set will be included in the OS analysis.

